I confirm that I have read this protocol, I understand it, and I will work according to this protocol and to the ethical principles stated in the latest version of the Declaration of Helsinki, the applicable ICH guidelines for good clinical practices, and the applicable federal, state, and local laws, rules, and regulations relating to the conduct of the protocol. I have read and understand the information in the Investigators' Brochure (or Manufacturer's Brochure) regarding the risks and potential benefits. I will promptly submit the protocol to the applicable IRB for review and approval. Once the protocol has been approved by the IRB, I understand that any modification made during the course of the study must first be approved by the IRB, prior to implementation except when such modification is made to remove an immediate hazard to the subject. I certify that I, and the study staff, have received the requisite training to conduct this research protocol. I agree to maintain adequate and accurate records in accordance with Columbia University and Herbert Irving Comprehensive Cancer Center policies, Federal, state and local laws and regulations. I agree to maintain the confidentiality of all information received or developed in connection with this protocol.

Instructions to Principal Investigator: Sign and Date this signature page and print your name.
Return the original, completed and signed to the Clinical Protocol & Data Management Office.
Retain a copy in the regulatory binder.

Signature of Principal Investigator

Date

Principal Investigator Name (Print)

Name of Institution

Protocol Synopsis

Title	A randomized phase 2 study of anti-IL-8 therapy versus standard of care in the treatment of hospitalized patients with severe COVID-19
Short Title	Anti-IL-8 for patients with COVID-19
Protocol Number	AAAS9881
Phase	Phase 2
Methodology	Randomized, open label, phase 2 study
Study Duration	12 months (estimated)
Study Center(s)	single-center
Objectives	
Primary:
 
• To determine the time to improvement in the 7-point ordinal scale in patients treated with anti-IL-8 therapy compared to standard of care/controls.
○ Measured from baseline to 2 point or greater improvement in 7-point ordinal scale. 
Secondary:
 
• To evaluate the time to death in patients treated with anti-IL-8 therapy compared to controls.• To evaluate the mortality 1 month after start of treatment in patients treated with anti-IL-8 therapy compared to controls.• To determine the time to intubation in patients treated with anti-IL-8 therapy compared to controls.
○ Measured from time of disease onset to time of intubation.• To estimate the time to improvement in oxygenation in patients treated with anti-IL-8 therapy compared to controls..
○ Measured as time from start of treatment until $\geq 30\%$ decrease in oxygen requirement compared to baseline• To measure the proportion of patients requiring ICU admission at 1 month in patients treated with anti-IL-8 therapy compared to controls.
○ Measured as the number of patients requiring ICU admission over their hospitalization over the number of evaluable patients.

	
• To compare the raw 7-point ordinal scale scores at day 14 in patients treated with anti-IL-8 therapy versus controls.• To assess the safety and tolerability defined as adverse events graded by CTCAE v5.0 in patients treated with anti-IL-8 therapy compared to controls.• To assess the duration of hospitalization in patients treated with anti-IL-8 therapy compared to controls.
○ Measured as time from admission to time of discharge.
Exploratory:	
• To assess the change in LDH, D-Dimer, CRP, ESR, NLR and absolute lymphocytes before and after treatment and over time (every 2 days for duration of hospitalization).• To assess the change in sIL-6 before and after treatment and over time.• To evaluate radiological response by comparing % of lung fields with infiltrates on chest imaging (CXR and CT) through independent radiology review.• To measure time on ventilation measured from time of intubation to time of definitive extubation• To measure time to improvement in NEWS2 score to ≤ 2• To evaluate the change in NEWS2 from baseline.• To measure proportion of patients with multi-organ failure at 1 month.• To assess whether IL-8 and other key cytokines (TNF, IL-1b, IL-6) at baseline and during treatment are predictive of treatment efficacy by quantification of circulating IL-1b, IL8, TNFalpha and IL-6 levels over time.• To quantify changes in humoral immune responses by antibody profiling at baseline and following treatment.• To characterize PK of BMS-986253 in cancer patients with severe COVID-19.

Diagnosis and Main Inclusion Criteria	Main Inclusion Criteria 
Confirmed diagnosis of SARS-CoV-2 infectionInpatient hospitalization due to SARS-CoV-2 infectionSevere (oxygen saturation $\leq 93\%$ on room air or requires $\geq 2\text{L}$ oxygen by NC in order to maintain $\text{SaO}_2 \geq 93\%$) OR critical respiratory disease (ICU, ventilatory support, HFNC)Non-COVID-related life expectancy > 2 monthsWillingness to provide informed consent
Study Product, Dose, Route, Regimen	BMS-986253 2400mg IV at 0 and 2 weeks (if patient is still hospitalized) and then 4 weeks (only if continued severe respiratory disease).
Duration of administration	Every 2 weeks x 1-3 doses.
Reference therapy	Standard of care management
Statistical Methodology	This is a single center, randomized, open-label, phase 2 trial to evaluate the time-to-improvement in the 7 point ordinal scale following treatment with BMS-986253 compared to standard of care in hospitalized patients with COVID-19 respiratory disease. With a sample of 138 patients (N=92 patients randomized to the treatment arm and N=46 patients assigned to the control/standard of care arm), the study will have 80% power to detect an increase in the median time to improvement from 5 days (control) to 2 days (anti-IL-8 arm) with one-sided alpha of 0.025. The sample size was estimated based on a hazard ratio (HR) of 0.40 assuming an exponential survival.
Interim Analysis	One interim analysis is planned once 17 (40% of the total 41 events) have been observed using O'Brien and Fleming stopping boundary using the Lan-DeMets spending function and inflation for drop-outs. The intent-to-treat (ITT) principle is applied to the analysis, and therefore, we inflated the sample size by 5% to safeguard against drop-outs/lost-to-follow-up.

Protocol Schema:

Contents

Protocol Signature Page	4
1. Introduction	12
2. Study Objectives	12
Primary Objective	12
Secondary Objectives.....	12
2.1 Exploratory Objectives	13
3. Background	13
3.1 Disease Background.....	13
3.2. IL-8 is a key cytokine in the pathogenesis of coronavirus-associated ARDS.....	14
3.3. Rationale for anti-IL-8 therapy in hospitalized patients with severe COVID-19.....	15
Investigational AgentS	15
3.4 BMS-986253	15
4. Study Design	20
4.1 General Design.....	20
4.2 Number of Subjects.....	21
5. Subject Selection and Withdrawal	21
5.1 Inclusion Criteria	21
5.2 Exclusion Criteria	23
5.3 Inclusion of Women and Minorities	23
5.4 Subject Recruitment.....	23
5.5 Early Withdrawal of Subjects	24
6. REGISTRATION PROCEDURES	25
6.1 CUMC Research Participant Registration	25
6.2 Informed Consent Procedures.....	26
7. TREATMENT PLAN	27
7.1 Agent Administration.....	27
7.2 Management of Infusion Reactions:	28
7.3 General Concomitant Medication and Supportive Care Guidelines	29
7.4 Treatment Compliance.....	29
7.5 Randomization and Blinding	29
7.6 Duration of Therapy.....	30
7.7 Duration of Follow Up.....	30
7.8 Criteria for Removal from Study	30
DOSING DELAYS/ DOSE MODIFICATIONS.....	30
7.9 Criteria and Procedures for Dose Modifications and Interruptions	30

8.	ADVERSE EVENTS: LIST AND REPORTING REQUIREMENTS	32
8.1	Adverse events	32
8.2	Definitions.....	33

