3.3. Rationale for anti-IL-8 therapy in hospitalized patients with severe COVID-19

BMS-986253 (also referred to as anti-IL8 mAb or HuMax IL8) is a fully human-sequence IgG1κ mAb directed against human interleukin-8 (IL-8) also known as CXCL8. IL-8 is a well-described pro-inflammatory cytokine orchestrating the recruitment of neutrophils in tissue injuries. BMS-986253 potently binds to and neutralizes the various biological activities of IL-8. BMS-986253 was initially investigated for the treatment of inflammatory skin diseases and demonstrated an excellent tolerability and safety. More recently, BMS-986253 has been developed as a cancer immunotherapy and is currently in late-stage phase 1 testing. Results from these studies show excellent safety and tolerability at a dose of 2400mg every 2 weeks in a cancer patient population.

Given the central role of IL-8 in the pathophysiology of ARDS, the increased morbidity and mortality of patients who develop severe COVID pneumonia and the excellent safety profile of BMS-986253, we believe there is an urgent need to evaluate this agent in patients who develop respiratory failure in the setting of SARS-CoV-2 infection. As a New York City based hospital, we believe we are well placed to rapidly evaluate BMS-986253 in this patient population.

INVESTIGATIONAL AGENTS

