5.2 Exclusion Criteria

- Treatment with anti-IL-6, anti-IL-6R antagonists or Janus kinase inhibitor (JAKi) within 48 hours of first dose of study treatment.
- No other investigational therapies as part of another clinical trial with the intent to treat the patient's COVID-19 can be administered while the patient is enrolled in the study.
 - Exception is remdesivir, hydroxychloroquine, convalescent plasma or other treatments being used as compassionate use or under Emergency Use Authorization (EUA) for COVID-19 per Investigator discretion.
- Expected non-COVID-related survival of < 2 months.
- Receipt of non-oncology vaccines containing live virus for prevention of infectious diseases within 4 weeks prior to first dose of study treatment
- History of severe hypersensitivity reaction to any mAb
- Multi-organ failure requiring vasopressors or continuous veno-venous hemofiltration (CVVH) or extracorporeal membrane oxygenation.
- No active systemic bacterial or fungal infection
 - Excludes patients with positive blood cultures not infections like empiric pneumonia, antibiotic coverage, UTIs, etc.
 - Patients with a history of positive bacterial or fungal cultures but on enrollment do not have suspected or known active systemic bacterial or fungal infections are permitted.

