7. TREATMENT PLAN

7.1 Agent Administration

Treatment will be administered on an inpatient basis. Reported adverse events and potential risks for BMS-986253 are described in **Section 10**. Appropriate dose modifications for BMS-986253 are described in **section 9**. No investigational therapies other than those described below may be administered with the intent to treat the patient's COVID-19 while the patient is enrolled in the study.

REGIMENT DESCRIPTION					
Agent	Premedications; Precautions	Dose	Route	Schedule ⁺	Cycle Length
BMS-986253	No specific premedications or precautions	2400mg	IV over 120 minutes (+/- 10 minutes)*	Days 1, 15, 29	6 weeks

*Infusion time will be 180 minutes (+/- 10 minutes) for patients <35kg.

⁺ Day 15 dose will be given if still hospitalized; day 29 dose is optional and will be given if patient hospitalized with severe respiratory symptoms.

7.2 Management of Infusion Reactions:

Since BMS-986253 contains only human Ig protein sequences, it is unlikely to induce hypersensitivity reactions. In the CA027-001 study, an infusion reaction (Grade 1) was observed in 1 patient and in the CA027-002 study 2 patients experienced infusions reactions (1 patient with Grade 2; 1 patient with Grade 4). If such a reaction were to occur, it might manifest with fever, chills, rigors, headache, rash, pruritus, arthralgia, hypotension, hypertension, bronchospasm, or other allergic-like reactions. All serious infusion reactions should be reported to BMS. All Grade 3 or 4 infusion reactions should be reported within 24 hours (excluding holidays and weekends) to the CUMC Sponsor-Investigator and BMS Medical Monitor and reported as an SAE. Infusion reactions should be graded according to NCI CTCAE v5.0 guidelines.

Treatment recommendations for infusion reactions are provided below and may be modified based on local treatment standards and guidelines, as appropriate.

For Grade 1 symptoms (mild reaction; infusion interruption not indicated; intervention not indicated):

- Remain at bedside and monitor participant until recovery from symptoms. The following prophylactic pre-medications are recommended for future infusions: diphenhydramine 50 mg (or equivalent) and/or acetaminophen/paracetamol 325 mg to 1000 mg at least 30 minutes before study treatment administrations.

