7.3 General Concomitant Medication and Supportive Care Guidelines

7.3.1 Concomitant Therapy

The following medications are prohibited during the study if the subject is randomized to the investigational therapy arm (unless utilized to treat a drug related AE):

- anti-IL-6, anti-IL-6R antagonists or Janus kinase inhibitor (JAKi)

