7.5 Randomization and Blinding

Patients will be randomized 2:1 (anti-IL8: standard of care) in “real-time”. If the subject’s eligibility status is confirmed, the statistician will send the randomization assignment based on the pre-generated randomization scheme.

This is an open-label study.

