11.2.16 Change in humoral immune response

The humoral immune response will be assessed by protein microarray antibody profiling at baseline and at additional time points when possible (day 8, 15, 22, 29).

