13.2 Study Endpoints and Analysis Plan

All subjects who receive at least one dose of study drug will be considered evaluable and included in the efficacy and safety analysis.

Analytic plan for primary objective:

The primary efficacy null hypothesis of the equality of time to improvement (2 points) in clinical status curves will be tested with the log-rank test. The overall type I error for the primary analysis will be considered one-sided alpha of 0.025. Kaplan-Meier estimates will be reported for each of the two arms with median time to improvement and 95% confidence intervals (CI). Cox regression will be employed to estimate the treatment effect (HR) and 95% CI.

Analytic plan for secondary and exploratory objective:

We will estimate the distributions of all time-to-event endpoints using the Kaplan-Meier method and if possible, provide medians (95% CI). Comparisons between survival curves will be assessed using log-rank tests and Cox regression models.

For each arm, we will estimate the 1-month mortality rate and incidence of adverse events graded by CTCAE v5.0 using the exact 95% confidence intervals. Comparisons between the two arms will be assessed using chi-squared or Fisher's exact tests. The mean/medians of the 7-point ordinal scores at day 14 after the start of treatment will be computed and compared between the two groups using two-sample t-test or the equivalent non-parametric Wilcoxon Rank-Sum test if normality is not satisfied.

Changes in exploratory endpoints (before and after treatment) will be quantified using means (95% CI) and/or medians (inter-quartile ranges) for non-normal data. Comparisons between the two arms will be made using two-sample independent t-tests or the non-parametric equivalent, Wilcoxon Rank-Sum test. The associations between baseline levels and/or changes over time of IL-8 and other key cytokines (TNF, IL-1b, IL-6) with outcomes will be assessed using regression models.

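### The exploratory humoral-response analysis counts donor antibody from convalescent plasma given after baseline as the patient's response; a sensitivity analysis should be pre-specified

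*Combined protocol and SAP*

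**What the plan says.** The Protocol Synopsis and section 2.1 list the exploratory objective "To quantify changes in humoral immune responses by antibody profiling at baseline and following treatment". Section 11.2.16 sets the method: "The humoral immune response will be assessed by protein microarray antibody profiling at baseline and at additional time points when possible", the later points being days 8, 15, 22 and 29. Neither the antigens on the array nor the readout is stated. The notes to the study calendar in section 10 make the serum samples desirable rather than mandatory.

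Section 13.2 summarises changes in exploratory endpoints by means or medians and adds: "Comparisons between the two arms will be made using two-sample independent t-tests or the non-parametric equivalent, Wilcoxon Rank-Sum test". It gives no covariate, exclusion or censoring rule for co-treatment.

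On co-treatment, section 5.2 bars other trial therapies for COVID-19 and then says: "Exception is remdesivir, hydroxychloroquine, convalescent plasma or other treatments being used as compassionate use". The exception extends to emergency use authorization and is left to investigator discretion. Section 7.1 states a ban without that exception: "No investigational therapies other than those described below may be administered with the intent to treat the patient's COVID-19". The list in section 7.3.1, introduced by "The following medications are prohibited during the study if the subject is randomized to the investigational therapy arm", names only anti-IL-6 and anti-IL-6R agents and JAK inhibitors. Section 7.5 adds: "This is an open-label study".

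Section 3.3 describes BMS-986253 as a fully human IgG1 kappa antibody against IL-8.

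**The concern.** Convalescent plasma carries donor antibody. A serum array read after a transfusion measures donor and patient antibody together, and nothing in sections 11.2.16 or 13.2 separates them. The reported change from baseline is then partly a record of who was transfused.

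Within an arm, this overstates the humoral response whenever any patient receives plasma between the baseline and a later sample. Between arms, it matters if plasma use or timing differs. Physicians know the allocation and plasma is discretionary. Section 7.3.1 already restricts some alternatives in the investigational arm only, so use could drift apart in either direction. A reader could then be told that blocking IL-8 dampens or raises antibody formation when the difference reflects transfusion.

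A related question concerns the drug itself. If the array includes IL-8 as a target, drug in the serum could register there as an anti-IL-8 antibody, in the treated arm only.

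**Working it through.** The plan gives no sample size, effect size or error rate for this endpoint, so there is no figure to reproduce. The check has three parts.

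**1. The text.** Plasma is permitted (5.2). Serum antibody is measured after baseline (11.2.16). The change is summarised and compared unadjusted (13.2). No section excludes, censors, stratifies or adjusts for recipients. Donor antibody given after baseline therefore enters the change score.

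**2. Size of the distortion.** Let *d* be the shift plasma adds to a recipient's change, in SD units, and let *p*T and *p*C be the proportions of treated and control patients given plasma after baseline.

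- Within-arm overstatement = *p* × *d*. With *p* = 0.30 and *d* = 1, this is 0.30 SD.
- Spurious between-arm difference = (*p*T − *p*C) × *d*. With 0.30 and 0.30 it is 0. With 0.20 and 0.40 and *d* = 1 it is −0.20 SD.

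From the documents: 138 patients randomized 2:1, hence 92 versus 46 (section 13.1). Assumed, because the documents give no figure: *p*T, *p*C, *d*, normally distributed changes with SD 1, no true drug effect, a two-sided 5% t-test, and a half-sampled scenario of 46 versus 23. Each rate comes from 20,000 simulated trials.

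| Plasma use, treated vs control | n | False rejection, *d* = 0.5 | *d* = 1 | *d* = 2 |
|---|---|---|---|---|
| 30% vs 30% | 92 vs 46 | 5% | 5% | 5% |
| 20% vs 30% | 92 vs 46 | 6% | 8% | 14% |
| 20% vs 40% | 92 vs 46 | 8% | 18% | 39% |
| 10% vs 40% | 92 vs 46 | 13% | 34% | 74% |
| 20% vs 40% | 46 vs 23 | 7% | 12% | 22% |

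Reversing the imbalance reverses the sign of the difference and leaves the rates similar. The 92 versus 46 rows assume that every patient has paired serum, which the optional sampling makes unlikely. Fewer samples lower the false-rejection rate but leave the bias in the mean unchanged.

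**3. Does dropping recipients cure it?** Not fully. Plasma is given after randomization and may go to patients who are responding poorly. The case simulated was 92 versus 46, 10% versus 40% use, no drug effect and recipients excluded entirely. With an assumed correlation of 0.3 to 0.5 between a low own response and receiving plasma, the false-rejection rate is about 9% to 18%. At zero correlation it is 5%.

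**The case against.** The strongest reply is that the documents show no imbalance. They give no plasma usage rate, and an open label makes unequal use possible rather than likely. Every error rate above is a product of chosen inputs, and the larger ones come from a fourfold difference in use. This stands. A reader might infer that the arm comparison will show a false difference; the documents do not support that, and with equal use the test keeps its 5% level.

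A reader might also infer that the drug's own IgG contaminates the endpoint. That is not established. It would need an IL-8 feature on the array, or a readout of total IgG, and section 11.2.16 states neither. The tissue study in section 3.4.2 found no specific staining of normal human tissue by the hybridoma-derived antibody, so a wider off-target signal has no support. Only a conditional remark survives.

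A further reply is that section 7.1 may already bar plasma. That shows two sections in conflict; it does not cancel the explicit exception in 5.2.

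It is also fair to say that the objective does not specify the patient's own antibody and names no comparison with controls. The comparison comes from the general sentence in section 13.2. Still, a humoral immune response is hard to read as including transfused antibody, and 13.2 does apply to this endpoint.

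Finally, the endpoint is one of ten exploratory objectives with no decision attached. That limits the severity but does not remove the point.

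**Conclusion.** The point holds in limited form. As written, sections 11.2.16 and 13.2 mix donor and patient antibody for anyone given convalescent plasma after the baseline sample. The within-arm change is overstated by the proportion of recipients times the plasma shift. The between-arm comparison is biased only by a difference in use or timing, at (*p*T − *p*C) × *d*. Illustrative false-rejection rates run from 5% with equal use to 39% at 20% versus 40% use with a 2 SD shift, and higher under more extreme imbalance. All rest on assumed usage, shift and SD.

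The IL-8 remark depends on array content that is not stated. Primary, secondary and safety conclusions are untouched. Severity is minor: this is a cheap improvement to an exploratory analysis.

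**What to change.** In sections 11.2.16 and 13.2:

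- Report the comparison on all samples, and beside it a pre-specified analysis that leaves out serum drawn after any convalescent plasma.
- Take transfusion dates from the daily medication review in section 10.2, and state that plasma, as a blood product, is to be recorded there with its date.
- Give the number of recipients and the timing of plasma relative to baseline, by arm.
- State that plasma use is a post-randomization choice, so the restricted analysis may carry selection bias. Neither analysis should stand alone.
- State the array content. If it includes an IL-8 feature, leave that feature out of the treated-versus-control comparison.

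Separately, reconcile sections 5.2 and 7.1 on whether convalescent plasma is allowed during the study.

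The cost is a few sentences, with no new visit or sample. The restricted analysis has fewer samples, and patients given plasma before the baseline draw contribute nothing to it.
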